The participant's medical history will include an assessment of their medication use, smoking history, and how often they rely on their rescue medication (at rest and with exertion). Any participation in a Rehabilitation Program will be captured as well.

Participants will be allowed to begin exercise assessments 15 minutes after their bronchodilator administration. Concomitant medication and any adverse events will be recorded. The Participants oxygen level will be monitored during the standard 6MWT by continuous finger pulse oximetry. If the participant is not currently prescribed and using supplemental oxygen and their oxygen level is

Pilot Study to Assess the Effect of Providing Intermittent Positive Airway Pressure in COPD Patients in Order to Relieve Their Exertion Related Shortness of Breath

HRC-17007-VBIDEPILOT-PN

consistently \leq 88% during the test, the test will be stopped and the participant will be excluded. If the participant is currently prescribed and using supplemental oxygen during the test and their oxygen level consistently falls \leq 88%, supplemental oxygen will be titrated during the test by trained study staff until their oxygen level persistently is at 90% or higher during the test. Oxygen equipment will be available at the sites.

We will follow the American Thoracic Society Statement Guidelines for the Six-Minute Walk Test which include the following criteria for immediately stopping a 6MWT: Intolerable dyspnea, leg cramps, staggering, diaphoresis, and pale or ashen appearance.

Device Training

Participants will be asked to train on the VitaBreath device to practice breathing with it. The purpose of this training period is to get the participant acclimated to the device prior to using it during the modified 6MWTs at the Study Intervention Visit. If the participants have trouble coordinating with the device or cannot tolerate the mouthpiece resulting in leaks from the nasal cavity, they will be excluded from the study.

All participants will also be asked to practice pursed lip breathing with proper instruction and training by site staff.

Randomization

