If the participant qualifies for the study, their device usage order (VitaBreath or control condition/ pursed lip breathing) will be randomized using a permuted-block randomization sequence at the study intervention visit. Each participant will complete two modified 6MWTs during the Study Intervention Visit, one with each therapy in a randomized order. The randomization will be stratified within each site.

Sites will use a randomization schedule in order to randomize the patients.

The Study Intervention Visit will be scheduled within 5 ± 2 business day period of Screening Visit/s.

Study Intervention Visit – Modified 6MWT

During the study intervention visit, the participants will first complete the Chronic Respiratory Questionnaire (CRQ)³³- initial (CRQ) (Appendix C). This survey will be completed by participants before they use the device during the modified 6MWT. The response to this questionnaire will serve as a baseline measurement.

At the Study Intervention Visit, WOCP will complete a pregnancy urine test prior to any usage of the VitaBreath study device.

Participants will be asked to practice breathing again with the VitaBreath device to get acclimated prior to using it during the modified 6MWTs at the Study Intervention Visit. Such use will be for a maximum time of 5 – 10 minutes. The coordinator will also remind the participant to practice Pursed Lip Breathing.

Pilot Study to Assess the Effect of Providing Intermittent Positive Airway Pressure in COPD Patients in Order to Relieve Their Exertion Related Shortness of Breath

HRC-17007-VBIDEPILLOT-PN

The participants will be asked to wait 30 minutes after using the device to wash-out any effects of training with the device before starting the 6MWT.

The coordinator will assess AEs or medication changes since the last visit. Resting Heart Rate and Blood pressure will be checked before the 6MWTs.

Participants will be asked to take their short acting bronchodilator medication after the device training, but only before the first walk test. Participants will be allowed to begin assessments 15 minutes after their bronchodilator administration. Concomitant medication and any adverse events will be assessed. If additional uses of the bronchodilator are required by participants during the in lab study, that use will be recorded / documented. Participant's blood oximetry levels will be monitored via pulse oximeter at all times.

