A medically trained clinician will be present during the test in case of adverse events.

Participants will be asked to perform two 6MWT assessments on the Study Intervention Visit. Borg assessments will be made prior to the start of each test.

For one of the tests, participants will be given the VitaBreath device and the other test will be with control condition, where the patients will be instructed to use pursed lip breathing. The order of these two tests will be randomized.

Test Procedure

In order to standardize the participant use of the devices, at the 3 minute mark the test will be stopped for 30 seconds. During this 30 second pause, study participants will be instructed to use the study device in order to help them recover from being short of breath. For the test where participants are randomized to not use a device, they will be instructed to use the pursed lip breathing technique to help them recover during the 30 second duration. After the 30 second pause, the participants BORG assessment will be made and then they will be instructed to complete the remaining 3 minutes of the walk test. At the end of the test, participants will be asked to sit down and their Borg assessment will be made every 30 seconds until they reach their baseline Borg.

Participants will be required to rest at least 30 minutes between tests.

Statistical and Analytical Plan

Descriptive Data

Descriptive data tables will be provided for all variables of interest. Continuous data will be presented by mean, standard deviation, median, minimum and maximum observation. Data will be presented in the untransformed and transformed format (if applicable) for each continuous variable. Categorical data will be presented as frequencies and percentages.

Pilot Study to Assess the Effect of Providing Intermittent Positive Airway Pressure in COPD Patients in
Order to Relieve Their Exertion Related Shortness of Breath
HRC-17007-VBIDEPILLOT-PN

Analysis Populations

The endpoint will only be analyzed among completed cases in this pilot study.

Primary Effectiveness Analysis

The data from this trial will be evaluated to determine whether they meet the assumptions of parametric methods. The distance walked during the modified 6MWT will be compared between VitaBreath and pursed-lip breathing, using either a paired t-test or the nonparametric Wilcoxon Signed Ranks test, depending on the distribution of the data. The significance level will be a two-sided alpha of 0.05.

Safety Analysis

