The incidence of adverse events will be tabulated in the descriptive statistics and compared between the treatment conditions.

Subject Accountability and Missing Data

It is expected that the number of subjects who will withdraw early from this pilot study will be small. The number and proportion of subjects eligible for and compliant with the final examination will be presented. Subjects who withdraw from the study will be tabulated with the reasons for the withdrawal. The endpoint will only be analyzed among completed cases in this pilot study, and therefore data will not be imputed for missing values.

Interim Analysis

There is no interim analysis planned for this study.

Statistical Software

The statistical analyses will be done using SAS, SPSS, StatXact, or Systat. Each of these software packages provides special features that will be exploited to provide a comprehensive analysis with excellent graphics support.

RISK AND DISCOMFORTS

The FDA has determined that this study is significant risk due to the target patient population. VitaBreath is intended to be an adjunct therapy for COPD participants to utilize for relief of their dyspnea after exertion that can consequently allow them to be more active. VitaBreath delivers intermittent non-invasive positive pressure (PAP) therapy that provides positive airway pressure of 18 cm H₂O during inspiration (IPAP) and 8 cm H₂O on expiration (EPAP), with a handheld device to COPD participants.

Pilot Study to Assess the Effect of Providing Intermittent Positive Airway Pressure in COPD Patients in Order to Relieve Their Exertion Related Shortness of Breath

HRC-17007-VBIDEPILLOT-PN

We believe that although there may be discomforts associated with the use of this device, all of the study devices have been tested to help ensure safety. Should the equipment not perform as designed, ventilation could increase or decrease more than desired. This effect could be uncomfortable. The participant can easily remove the device should it become uncomfortable or make breathing difficult. Other potential side effects may include ear discomfort, and gastric distension (aerophagia), all of which are quite uncommon, but generally cited side effects of PAP therapy.

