Monitoring will be conducted by the sponsor to assure adherence to the protocol, Institutional Review Board requirements, and reporting and investigation of serious adverse events. The site investigator will evaluate and classify events. An adverse event (AE) is a situation in which the participant experiences illness or injury not addressed in the device labeling, research protocol, or research consent form. All AEs will be recorded on the AE log provided in the site binder.

A serious adverse event (SAE) is an adverse event:

- Resulting in death, or
- Resulting in a serious deterioration in the health of the subject that:
 - Results in a life-threatening illness or injury,
 - Results in a permanent impairment of a body structure or body function,
 - Requires inpatient hospitalization or prolongation of existing hospitalization, or
 - Results in medical or surgical intervention to prevent permanent impairment of a body structure or body function.

Participants will report any AEs or SAEs to the research staff (i.e., investigators and study coordinators) in the course of scheduled and non-scheduled participant contacts (i.e., clinic visits, phone calls, and emails). All events will be reported to the sponsor by the research staff; however, all SAEs must be reported to the sponsor within 24 hours of discovering the occurrence of the SAE. The research staff is required to complete and submit the sponsor's standard SAE form detailing the event.

REFERENCES

Pilot Study to Assess the Effect of Providing Intermittent Positive Airway Pressure in COPD Patients in Order to Relieve Their Exertion Related Shortness of Breath

HRC-17007-VBIDEPILOT-PN

4. O'Donnell DE. Exertional breathlessness in chronic respiratory disease. In; DA Mahler, ed. *Dyspnea*. New York, Dekker, 1998; pp. 97-147.

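### The only planned safety analysis compares adverse events between two walks that differ by one 30-second device use, so most device exposure, which is training given to everyone, falls outside the comparison

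*Combined protocol and SAP*

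**What the plan says.** - **Analysis.** The Safety Analysis paragraph of the Statistical and Analytical Plan reads in full: "The incidence of adverse events will be tabulated in the descriptive statistics and compared between the treatment conditions". It gives no safety population, event window or attribution rule. The completed-case restriction under Analysis Populations is stated for the endpoint only.
- **Screening training.** Under Device Training, all participants practise with VitaBreath, for an unstated time. Of those who cannot coordinate with it or tolerate the mouthpiece, the protocol says "they will be excluded from the study". Randomization comes later, at the Study Intervention Visit.
- **Visit training.** At that visit, "Participants will be asked to practice breathing again with the VitaBreath device to get acclimated prior to using it during the modified 6MWTs". On duration: "Such use will be for a maximum time of 5 – 10 minutes". A 30-minute wait follows.
- **Walks.** Under Test Procedure, "at the 3 minute mark the test will be stopped for 30 seconds". For the VitaBreath walk, "During this 30 second pause, study participants will be instructed to use the study device"; in the other walk the pause is spent on PLB. Each participant does both walks at one visit in random order, at least 30 minutes apart.
- **Event collection.** At the intervention visit, "The coordinator will assess AEs or medication changes since the last visit". The same section also has events assessed during the visit. Under Monitoring and Quality Assurance, participants report events to staff "in the course of scheduled and non-scheduled participant contacts". No contact is scheduled after the Study Intervention Visit.

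**The concern.** A comparison between conditions is informative about device safety when the device exposure lies mainly in one of them. Here the randomized contrast is 30 seconds of use against none, while the longer exposure is shared by everyone and precedes both walks. A device-related event that starts in training, or in a wait, has no assigned place in the comparison. When VitaBreath comes first, a late event can surface in the PLB period.

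Two groups of events are harder still to capture. People who fail training have used the device but are never randomized, so a table by condition has no column for them. Events that begin after the intervention visit depend on the participant making contact.

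At stake is whether the pilot's safety table describes the device or only one half-minute of its use. The protocol states that FDA classed the study as significant risk, and the planned pivotal trial has the same two conditions.

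**Working it through.** The documents give no event rate, exposure share or safety power, so there is no stated figure to reproduce.

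**1. Share of visit device time spent in training.** Inputs: training time T of at most 5–10 minutes (Study Intervention Visit section); walk use 0.5 minutes (Test Procedure). Share = T/(T + 0.5).
- T = 5: 5/5.5 = 90.9%; the walk is 0.5/5.5 = 9.1%.
- T = 10: 10/10.5 = 95.2%; the walk is 0.5/10.5 = 4.8%.

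**2. Sensitivity.** The 5–10 minutes is a maximum and no minimum is given. For assumed shorter training the share is 1/1.5 = 66.7%, 2/2.5 = 80.0% and 3/3.5 = 85.7%. If screening training is added at an assumed 5 or 10 minutes, it is 10/10.5 = 95.2% or 20/20.5 = 97.6%.

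**3. Dependence on the missing rule.** Illustrative assumptions: 20 participants, device-caused events only, a constant hazard of 0.02 per minute of use, balanced order, visit training only. Expected participants with an event = 20 × (1 − exp(−0.02 × minutes)).
- Training: 1.90 (5 min) or 3.63 (10 min).
- Walk use: 0.20.

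Expected participants with an event, VitaBreath vs PLB:

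| Where training events go | 5 min | 10 min |
|---|---|---|
| Neither condition | 0.20 vs 0 | 0.20 vs 0 |
| Both conditions | 2.08 vs 1.90 | 3.79 vs 3.63 |
| The walk that comes first | 1.14 vs 0.95 | 1.99 vs 1.81 |
| The device condition | 2.08 vs 0 | 3.79 vs 0 |

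The same events give four different tables. Under the first rule most device events leave the comparison. Under the second and third the ratio is close to 1: at 5 minutes, 2.08/1.90 = 1.09 and 1.14/0.95 = 1.20. Only the fourth shows all the device events as a difference. Hazards of 0.01 and 0.05 change the counts but not this pattern.

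**4. Who and what is not covered.** Screening use is followed by the since-last-visit check at the intervention visit, but someone excluded at screening training does not reach that visit. Use at the intervention visit, the last of the study, has no scheduled check after the visit ends.

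**The case against.** The strongest reply is that the plan tabulates events as well as comparing them. All events go on the log and to the sponsor, and the investigator evaluates and classifies them. Events are recorded at screening and assessed during the intervention visit, and a clinician is present for the tests. Nothing removes a training event from the overall tabulation. The 30-minute waits limit short-lived carryover, although nothing links them to attribution. This stands: the gap is in the comparison and in follow-up after the visit, not in logging during visits. It is also a 20-patient pilot in which a descriptive table is reasonable.

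A reader might infer several stronger things that the documents do not support:
- **That device events will look alike in both conditions.** This needs one of two particular attribution rules, and the plan states none.
- **That the comparison is biased towards no difference.** If all events are device-caused, proportional to minutes and split evenly by order, the 5-minute case gives 9.1 + 45.45 = 54.5% vs 45.5%. The difference, 9.1 points, is exactly the walk-caused share. Evenly split training events add noise and dilute the ratio, but do not bias the absolute difference in events. Exercise-related events, which can arise in both walks, are also ignored in that calculation.
- **That attribution affects the suspension rule.** The rule under Risk and Discomforts counts barotrauma and pneumothorax whatever the condition.
- **That visit use exceeds screening use.** Screening training has no stated duration.
- **That the upper limit for zero events in 20 proves the point.** That limit reflects sample size and says nothing about attribution.

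One limit on the remedy also stands. The protocol defines an adverse event as one not already addressed in the labelling, protocol or consent form. Read literally, listed effects such as ear discomfort would not be counted in any phase, and an onset-phase table would not recover them.

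**Conclusion.** The concern holds in a limited form. The stated comparison isolates 30 seconds of device use. At the stated training limits, 91–95% of visit device time lies outside it; this falls to 67–86% if training lasts only 1–3 minutes. Depending on a rule the plan does not give, device-related events from that larger exposure may drop out of the comparison or be attached to either walk, diluting a relative difference. Training failures belong to neither condition, and events beginning after the intervention visit have no scheduled check.

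The exposure shares rest only on the stated durations. The event counts rest on an assumed constant hazard and are illustrative. The size of any actual loss is unknown, because the documents give no event rate.

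**What to change.** 1. Define the safety set as everyone with at least one device use, including screening training and those excluded there. Make overall incidence in this set the main safety summary, with an exact 95% CI and investigator-judged device relatedness.
2. Tabulate events by onset phase: screening training, visit training, VitaBreath walk and its rest, PLB walk and its rest, and after the visit. State in advance how events in the waits are assigned.
3. Restrict the between-condition comparison to events starting in a walk or its rest. Label it descriptive and note possible carryover when VitaBreath comes first.
4. Report the number of training failures and the reasons.
5. Add one brief scripted adverse-event contact after the Study Intervention Visit.

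This is a cheap improvement. It needs SAP wording, one onset-phase field on the adverse-event log and about 20 short calls. The calls are a new procedure, so they require a small protocol change. The downside is a possibly less favourable safety table.

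### The adverse event definition, read literally, excludes harms named in the protocol's own risk section, and so keeps them out of the AE log, the SAE rule and the AE table

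*Combined protocol and SAP*

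**What the plan says.** The only definition of an adverse event is in Monitoring and Quality Assurance. It covers a situation in which "the participant experiences illness or injury not addressed in the device labeling, research protocol, or research consent form". Three provisions are built on the term:

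- **AE log** (same section): "All AEs will be recorded on the AE log provided in the site binder".
- **SAE definition and expedited report** (same section): "A serious adverse event (SAE) is an adverse event" that has one of a list of serious outcomes. On reporting: "All events will be reported to the sponsor by the research staff; however, all SAEs must be reported to the sponsor within 24 hours" of discovery.
- **Safety Analysis** (Statistical and Analytical Plan): "The incidence of adverse events will be tabulated in the descriptive statistics and compared between the treatment conditions".

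Risk and Discomforts names foreseeable harms at some length. For the device it says: "Other potential side effects may include ear discomfort, and gastric distension (aerophagia"). It then discusses barotrauma and pneumothorax as possible results of the delivered pressures. For exercise testing it lists, among others, dizziness, arrhythmias, chest pain, heart attack and syncope.

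**The concern.** A harm that the protocol discusses is, on any ordinary reading, addressed in the protocol. The definition therefore excludes the events that the sponsor considered foreseeable and captures only those that nobody wrote down. That reverses the usual purpose of AE collection, in which foreseeability is a property recorded about an event and not a condition for recording it.

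The stake is the safety record. Risk and Discomforts reports that the FDA classed the study as significant risk, and the AE table is its only planned safety analysis. A site that applied the definition as written could omit the expected device and exercise harms from the log, from the 24-hour report and from the comparison of VitaBreath with pursed lip breathing. The pressure-related harms are those that the protocol links to positive airway pressure. If they occurred and were omitted, the loss would plausibly fall more on the device condition. The study also prepares for a pivotal trial (Sample Size section), so the wording could be carried forward.

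**Working it through.** No figure in the plan depends on this definition, so there is nothing to recompute. The check sets the sections side by side.

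**1. Is there a wider definition elsewhere?** No. The Safety Analysis paragraph and the visit procedures use the term without defining it. The labeling is not among the documents, and the consent pages are not available. The protocol alone is enough, because being addressed in any one of the three sources takes an event out of the definition.

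**2. What is excluded?** Risk and Discomforts names ear discomfort, gastric distension, barotrauma, pneumothorax, arrhythmias, heart attack and syncope, among others. Each is an illness or injury, or would commonly be recorded as one, and each is discussed in the protocol.

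**3. What follows for each output?** Two examples trace the chain.

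- *Gastric distension after device use.* It is named in the protocol, so it is not an AE. The log takes AEs, so no entry is required. The table counts AEs, so it is not tabulated.
- *Heart attack during a walk, with hospital admission.* Hospitalization is one of the listed serious outcomes, but an SAE must first be an AE. The event is named as an exercise risk, so that first condition fails. Literally, it is neither an AE nor an SAE, and the 24-hour requirement does not attach.

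**4. Does the rest of the protocol use the term this way?** Four places suggest not.

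- Risk and Discomforts gives the suspension rule for barotrauma and pneumothorax and then turns at once to any *other* SAE. That implies that those two are SAEs.
- The stopping sentence in the same section adds *unanticipated* as a separate qualifier of a device-related adverse event. The word would add little if every AE were already unanticipated.
- The Study Intervention Visit section has a clinician present during the walk because adverse events might occur. That fits poorly with a term that excludes the exercise harms the protocol foresees.
- The Screening Visit section requires adverse events around the screening walk to be recorded, with no hint of a restriction.

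The simplest explanation is that the criterion for an *unanticipated* event was placed in the sentence that defines an AE.

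**5. Do other provisions close the gap?**

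- The suspension rule counts barotrauma and pneumothorax directly, so it operates whether or not they are AEs.
- The requirement that all events go to the sponsor helps, but it leaves *events* undefined, sets no deadline for non-serious events and requires no log entry.
- "The site investigator will evaluate and classify events" gives the investigator discretion, but within the stated definition.
- The coordinator's check for AEs since the last visit uses the same defined term.
- Oximetry, records of extra bronchodilator use, and the provision that "Subjects who withdraw from the study will be tabulated with the reasons for the withdrawal" would preserve some information, but none of it feeds the AE table.

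**6. Can the size be given as a number?** Not usefully. A count of excluded event types changes with whether paired items are merged, whether death is listed as an event, and whether malfunction effects, radiation risks and the signs for stopping a walk are included. The literal wording also reaches conditions mentioned outside the risk section, such as COPD exacerbation and unstable angina in the eligibility criteria, so a list drawn from the risk section alone has no firm upper end. The documents give no event rates, and they say that those for barotrauma and pneumothorax are not well defined.

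**The case against.** The strongest reply is that no sensible site would apply the sentence literally. The four places in step 4 point to a broader meaning, the sponsor is to receive all events, the investigator classifies them, and the AE log, SAE form and training may well prompt for anticipated events. This is also a small pilot of 20 patients with monitored walks and a primary endpoint of walking distance. Much of this stands: it makes a drafting slip the likely explanation and literal application less likely. It does not cure the sentence, which is the only definition given. Because monitoring checks compliance with the approved protocol, a site that left out a named harm could say that it had followed the text.

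It may also be said that heart attack and syncope are named only in connection with comorbidities, while the eligibility criteria exclude heart disease. This is weak: the text names both as risks of the exercise testing.

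Three stronger readings are tempting and are not supported:

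- *That Risk and Discomforts flatly contradicts the definition.* It never states that barotrauma or pneumothorax is an SAE. The inference rests on the single word *other*. It is a fair inference, and the sections need reconciling, but it is no more than that.
- *That the safety suspension rule is disabled.* It refers to the two events by name and does not depend on the AE definition.
- *That a stated number of event types, or of events, will be lost.* Step 6 shows why neither can be fixed.

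**Conclusion.** The concern holds as a defect of wording with a real consequence if the wording is followed. Read literally, the AE definition excludes harms that the protocol names, and the AE log, the SAE definition with its 24-hour report, and the only planned safety analysis all inherit the exclusion. This is a stated rule that is wrong, not a missing detail, and other parts of the protocol imply a broader meaning.

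The conclusion assumes that *addressed in the protocol* includes being named in its risk section, and that no wider definition exists in materials that cannot be seen. A reader might infer that harms were or will be under-reported; the documents do not show this, since the log, the SAE form and the training are not available. The suspension trigger, the walking-distance endpoint and the pilot's purpose of informing the pivotal trial's power are unaffected.

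**What to change.** - In Monitoring and Quality Assurance, delete the restriction from the AE definition, so that an AE is any untoward medical occurrence, whether or not it was anticipated and whether or not it is related to the device.
- Keep the present criterion (not addressed in the labeling, protocol or consent form) only as the test for calling an event unanticipated.
- Reconcile Safety Analysis, Risk and Discomforts, and Monitoring and Quality Assurance, so that the log, the SAE definition, the 24-hour report and the AE table all use this one definition.

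The suspension and stopping thresholds in Risk and Discomforts are outside this point and are left as they are. The change is a matter of a few sentences and needs no extra patients or visits. The cost is somewhat more AE recording at the sites and a reported AE count that may be higher.
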